6.4. Donor Liver Retrieval and OCS Preservation and Assessment

After final evaluation of the donor Liver in donor's abdomen and upon acceptance into the trial, the investigators will retrieve and preserve the donor Liver according to the following protocol:

- **Initial Liver Flush in Donor Body:** all donor Livers will be flushed using cold Belzer UW® solution or Custodiol® HTK preservation solutions according to the institution's standard of care practice and the manufacturer instruction for use.
- **OCS Liver Back Table Flush:** All donor livers randomized to be perfused on OCS Liver system will be flushed on the back table using cold PlasmaLyte® solution supplemented with sodium bicarbonate (NHCO3) 10 mmol/L, Epoprostenol Sodium 2 mics/L, and Methylprednisolone ~160 mg/L flush below, according to the following protocol:
 - **Hepatic Artery:** 1 liter flush at ~50-70 mmHg pressure bag
 - **Portal Vein:** 2 liters gravity drain
- **OCST™ Liver Perfusion:** The OCST™ Liver system will be primed using the following:

OCS Liver Perfusate Composition	Recommended Dose
Packed Red Blood Cells (pRBCs)*	4-8 units
Albumin 25%	400 mls
PlasmaLyte® solution	700-800 mls
Methylprednisolone	500 mgs

OCS Liver Perfusate Composition	Recommended Dose
Dexamethasone	20 mgs
Sodium Bicarbonate (NaHCO ₃) 8.4%	70 mmol
Adult Multivitamins for infusion e.g., INFUVITE®	1 unit
Calcium Gluconate 10% (100 mg/ml)	10 mls
Antimicrobials:	
Gram positive antibiotic e.g., Cefazolin	1 gm
Gram negative antibiotic e.g., Cirprofloxacin	100 mg
* type specific (or O negative blood group), pathogen free, leukocyte and platelet reduced	

- **OCSTTM Liver Perfusion Additives:** In addition to the above OCS Liver perfusate, the following will be infused to the perfusate mix using an ex-vivo solution pump:

OCS Liver Perfusate Additives	
Continuous Infusion Mix	Dose
Total parenteral nutrition (TPN) Mix: CLINIMIX E TPN (4.25% Amino Acid / 10% Dextrose); PLUS Insulin 30 IU Glucose 25 gms Heparin 40,000 units	30 ml/hr
As Needed Additives	Dose
Prostacyclin infusion as needed to control Hepatic artery pressure e.g., Epoprostenol Sodium 0.5 mg	0-20 mics/hr
Bile Salts e.g., Taurocholic acid sodium (1 gm/50 ml)	3 ml/hr
NaHCO ₃ 8.4% to correct metabolic acidosis	1.5 meq/1 base excess

- **Bile Salt Preparation:** All study sites will be provided sealed Gamma-sterilized vials of 1 gm of Taurocholic acid sodium in salt form to be mixed prior to retrieval according to the following steps::

- Add 50 ml of sterile water for injection using aseptic technique
- Mix well to ensure all salt is dissolved

At the time of use the OCS operator will spike the stopper of the vial using a sterile OCS infusion line and connect to the OCS infusion delivery system.

- **The OCSTTM Liver Preservation Parameters:** Donor livers will be perfused on the OCS Liver device with OCS parameters maintained within the following ranges
 - Hepatic Artery Pressure (mean HAP): 75-100 mmHg

- Hepatic Artery Flow (HAF): 300-700 ml/min
 - Portal Vein Pressure (mean PVP): 4-8 mmHg
 - Portal Vein Flow (PVF): 700-1700 ml/min
 - Perfusion Temperature (Temp): 34°C
 - Oxygen gas flow 400-700 ml/min
 - Circulating arterial Lactate (Lact) trend: trending down over time
- **Lactate and Liver Enzyme Levels During OCS Liver Perfusion Sampling Scheme:** The organ retrieval team will collect samples from the arterial port of the OCS perfusion circuit to measure lactate level using a standard blood analyzer according to the following protocol:
 - OCS Baseline arterial sample within the first 10-30 min of liver instrumentation.
 - Lactate
 - Liver enzymes: AST, ALT, GGT, total bilirubin, and ALP
 - Lactate samples will continue to be collected from the device at approximately hourly intervals until lactate level is trending down, at this time, lactate samples should be done every 2 hours or after any active HAF or HAP adjustments.
 - OCS Final arterial sample before cooling liver on OCS
 - Lactate
 - Liver enzymes: AST, ALT, GGT, total bilirubin, and ALP
- **Final Liver Cooling and Flush Arrest on OCS:** all donor Livers on OCS will be cooled and flushed on the OCS using cold PlasmaLyte® solution supplemented with sodium bicarb olone onate (NHCO3) 10 mm/L, Epoprostenol Sodium 2 mics/L, and Methylprednisolone 160 mg/L flush below, according to the following protocol:
 - **Hepatic Artery:** 1 liter flush at ~50-70 mmHg pressure bag
 - **Portal Vein:** 2 liters gravity drain
- **Liver Biopsy (see Appendix 1):** a needle biopsy will be collected from donor livers preserved on OCS or control on the back table, post preservation, immediately before re-implantation.
- **OCS Preservation Information:** the following information will be collected
 - Device Information (serial number etc.)
 - Device Malfunction(s)
 - OCS system data collected by the device during the preservation run and uploaded into the EDC database
- **Donor Retrieval Details:** The following information will be collected at time of Liver retrieval
 - Date and time of cross clamp of donor aorta

- **OCS Details (Liver Instrumentation details):**
 - Total cold ischemia time between initial donor cross clamp and start of OCS™ Liver perfusion
- **OCS Parameters and Enabled Measurements:** The following OCS™ Liver perfusion parameters and Liver metabolic conditions will be recorded:
 - HAP
 - HAF
 - PVP
 - PVF
 - Total Bile volume
 - OCS Liver arterial lactate level

6.5. Donor Liver Acceptance for Transplantation

All donor livers that are preserved on OCS or Control are expected to be transplanted into a matching consented recipient. Any decision to turn down Livers after the Livers have been retrieved, preserved on either OCSTM Liver or cold storage should be done with notification to the Site PI and the donor Liver examined by the transplant center's qualified liver transplant pathologist and/or tissue slides/samples to be sent to core lab for the study for further examination. All reasons for turning down a donor liver after it has been preserved will be collected in the eCRFs.

7. TRANSPLANT, IMMEDIATE POST-OPERATIVE AND LONG TERM FOLLOW-UP

7.1. Transplant Details

The following information concerning the transplant procedure will be collected:

- The organ recipient unique post-transplant patient identifier
- Total cross clamp duration in minutes (from donor cross-clamp application to removal of cross-clamp in the recipient)
- Total cold ischemia time will be collected (Control= total cross clamp time; OCS = cold ischemic time pre and post OCS Liver perfusion)
- Any surgical complications encountered during surgery
- Use of circulatory bypass will be recorded
- Type of liver anastomosis
 - Bicaval anastomosis; or
 - Piggyback anastomosis
- The total amount of any blood product and clotting factors transfusion will be collected (pRBCs, Fresh Frozen Plasma (FFP), platelets, etc.)

- Any inotropic support needed to maintain hemodynamics will be collected for both arms
- A liver tissue biopsy will be collected from Right lobe of the transplanted liver immediately before abdominal closure in the recipient. The biopsy will be collected according to Liver Biopsy protocol in [Appendix 1](#).

7.2. Post-transplant Functional Assessments Day 0 – Day 30:

- **Early Liver Allograft Dysfunction (EAD) Surveillance in the first 7 days:**
 - AST level >2000 IU/ml within the first 7 postoperative days;
 - Bilirubin ≥ 10 mg/dl on postoperative day 7;
 - INR ≥ 1.6 on postoperative day 7; or
 - Primary non-functioning graft within 7 days
- **Inotropic Support to Maintain Hemodynamics at T0, T24 and 48 and 72 hours after ICU admission (if applicable) will be collected**
- **Initial use of Mechanical Respiratory Support:** duration of initial post-transplant invasive ventilator support will be recorded from the time of initial admission to ICU post-Liver transplant until extubation.
- **Initial Post-Transplant ICU Stay:** Intensive care unit (ICU) admission time, and date and time when clinical order for ICU discharge is written.
- **Renal Replacement Therapy:** Need for dialysis treatments in the first 10 days post liver transplantation for patients that did not have renal replacement prior to transplantation
- **Immunosuppression Medications:** The type of immunosuppression medication and dose will be recorded at day 7 and at time of discharge from the hospital. Immunosuppression induction will be recorded if applicable.
- **Patient and Graft Survival at Day 30 and At Initial Hospital Discharge:** Patient and graft survival will be assessed on day 30 post-transplant and at initial hospital discharge post-liver transplantation.
- **Adverse Events:** All Liver graft-related serious adverse events and any Liver graft-related adverse events will be followed and documented until the investigator designates the event to be either resolved or its effect on the patient's condition stabilized.
- **Medications:** Medications used to treat all serious Liver graft-related adverse event (SAE)-related will be recorded in the trial electronic database until the SAE is resolved.

These follow-ups will be attempted within ± 3 days of the designated periods except for the Early Liver Allograft Dysfunction (EAD) Surveillance, in the first 7 days which must be collected at the designated times. The evaluations may be conducted over several days.

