Primary non-function rate	0 (0)	0 (0)
Early Allograft Dysfunction, n (%)	3 (15%)	9 (22.5%)
Peak AST within 7 days, (IU/L), median (range)	417 (84-4681)	902 (218-8786)
Initial Post-Tx. ICU stay (days), median (range)	3 (1-8)	3 (1-41)
Hospital Stay (days), median (range)	12 (6-34)	14 (8-88)

[figure not shown]
Source: Rising Star Symposium, International Liver Transplant Society, June 5, 2014, London, England; Abstract O-1, Human Liver Transplantation Using Normothermic Machine Preservation, Friend P, et al.
Sunrise Symposia; New Dimensions in Liver Transplantation, World Transplant Congress, July 31, 2014, San Francisco, CA, U.S.A.; Normothermic Machine Preservation of the Liver, Friend P, et al.

Based on the above overwhelming supportive pre-clinical, scientific and clinical evidence of safety, feasibility and potential benefits of warm machine perfusion for liver transplantation using identical perfusion protocols/perfusates to the OCS liver technology, we are proposing to proceed with a pivotal prospective clinical investigation of the OCS liver technology to compare its outcomes to cold static storage in liver transplant recipients.

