9.6. Sample Size Determination

The sample size for this trial was determined based on the primary effectiveness endpoint, Early Liver Allograft dysfunction (EAD) in the first 7 days post-transplantation. The sample size calculation assumed a one-sided, normal approximation test for non-inferiority, an alpha level of 0.05, a non-inferiority margin of 0.075, a 1:1 allocation, true proportions for the primary effectiveness endpoint of 0.2 for the OCS treatment and 0.25 for the Control treatment, and power of 80%. Based on these specifications, the required sample size was determined to be 144 transplanted recipients per treatment group, or 288 total transplanted subjects. To ensure an adequate number of subjects in the Per Protocol Population, the sample size was increased to a total of 300 transplanted subjects. Subjects will be enrolled until there are either 290 subjects in the Per Protocol Population or a total of 300 transplanted subjects, whichever comes first.

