6. ANALYSIS POPULATIONS

6.1. Per Protocol Population

The Per Protocol (PP) Population will consist of all randomized subjects who are transplanted and have no major protocol violations and for whom the donor liver received the complete preservation procedure as per the randomization assignment. The major protocol violations that will exclude a subject from this population are the following:

- Ineligible for the study according to the recipient inclusion and exclusion criteria
- Ineligible for the study according to the donor organ inclusion and exclusion criteria
- Subject is transplanted with a liver with preservation other than that to which the subject was randomized
- Failure to complete adequate post-transplant assessments to support the primary, secondary or safety endpoints
- Other major protocol violations

The final designation of major protocol violations resulting in an exclusion from the PP Population will be made during a blinded review by the CEC prior to database lock.

In analyses based on the PP Population, subjects will be analyzed as randomized. The primary analysis of the primary and secondary effectiveness endpoints and of other endpoints will be based on the PP Population.

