12. ANALYSIS OF EFFECTIVENESS ENDPOINTS

12.1. Primary Effectiveness Endpoint

The primary effectiveness endpoint for this study is Early Liver Allograft Dysfunction (EAD), defined as presentation of one or more of the following criteria:

- AST level > 2000 IU/ml within the first 7 postoperative days
- Bilirubin ≥ 10 mg/dl on postoperative Day 7
- INR ≥ 1.6 on postoperative Day 7
- Primary non-functioning graft within the first 7 days (defined as irreversible graft dysfunction requiring emergency liver re-transplantation or resulting in death, in the absence of immunologic or surgical causes)

The primary hypothesis for this study is that the OCS treatment is non-inferior to the standard of care treatment with respect to this endpoint. The primary statistical hypotheses are as follows:

$$H_{10}: \pi_{1,OCS} \geq \pi_{1,CONTROL} + \delta \text{ and}$$

$$H_{11}: \pi_{1,OCS} < \pi_{1,CONTROL} + \delta,$$

where $\pi_{1,OCS}$ and $\pi_{1,CONTROL}$ are the true proportions of subjects with Early Liver Allograft Dysfunction for the OCS and standard of care treatments, respectively, and δ is the non-inferiority margin, which is here taken to be 0.075.

The primary effectiveness endpoint will be analyzed by calculating, for each treatment group, the sample proportion of subjects meeting the primary effectiveness endpoint, as well as an exact (Clopper-Pearson) 95% confidence interval for the corresponding population percentage. The 95% exact unconditional one-sided upper confidence bound based on the Farrington and Manning score statistic will be calculated for the difference between the two population proportions ($\pi_{1,OCS} - \pi_{1,CONTROL}$). An upper confidence bound less than $\delta = 0.075$ will result in rejection of the null hypothesis (H_{10}) in favor of the alternative hypothesis (H_{11}) and the demonstration of non-inferiority of OCS to control for the primary effectiveness endpoint. In the event non-inferiority is demonstrated, Fisher's exact test (two-sided) will be used to test for superiority.

This endpoint will be analyzed using the Per Protocol and mITT Populations. The Per Protocol analysis will be considered the primary analysis. Analyses will first be performed without any imputation of missing data. If there are any missing data for this endpoint, multiple imputation methods will be used for data imputation for any patients with missing values for this endpoint. The multiple imputation methods are described in Section 5.3.

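### Bilirubin and INR count for EAD only on postoperative day 7, with no window and no rule for a missed or off-day sample, so the plan's missing-data routes can overstate EAD in the affected arm

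*Protocol*

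**What the plan says.** EAD (Protocol 4.1, 7.2 and 9.3.1; SAP 4.1 and 12.1) is present if any one of four criteria is met. AST above 2000 and primary non-function (PNF) count at any time in the first seven days. Bilirubin and INR count on a single day, "mg/dl on postoperative day 7" in the case of bilirubin.

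Protocol 7.2 allows ±3 days for the other follow-ups in that section but excepts "Early Liver Allograft Dysfunction (EAD) Surveillance, in the first 7 days which must be collected at the designated times". Appendix 2 lists EAD surveillance only in the column running from transplant to day 7. It gives no procedure for a recipient already discharged.

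On missing outcomes, SAP 12.1 states that "Analyses will first be performed without any imputation of missing data", with multiple imputation to follow. SAP 6.1 lists "Failure to complete adequate post-transplant assessments to support the primary, secondary or safety endpoints" among the violations that remove a subject from the Per Protocol Population, which carries the primary analysis; what counts as adequate is not defined. The imputation model in SAP 5.3 contains treatment, DCD status, donor age, steatosis, recipient gender and recipient age. The tipping-point analysis in SAP 5.4 penalises missing OCS outcomes only.

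Neither document says how EAD is derived when AST is 2000 or below and the day-7 bilirubin or INR is absent or off-day.

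**The concern.** The composite can be settled as positive without the day-7 values, but it cannot be fully confirmed as negative without them. A recipient with AST above 2000 or PNF has EAD whatever happens on day 7. A recipient with neither needs both day-7 values below threshold to be a documented negative. A missed or off-day sample, for instance after early discharge, can therefore make only the second kind of recipient undetermined.

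If undetermined recipients are set aside, the arm's EAD rate rises because its denominator loses mainly non-events. Where the loss differs between arms, the treatment difference is biased. Greater loss in OCS costs power; greater loss in Control makes a false finding of non-inferiority more likely.

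**Working it through.** **1. The plan's own figure.** Protocol 9.6 assumes "a one-sided, normal approximation test for non-inferiority, an alpha level of 0.05, a non-inferiority margin of 0.075, a 1:1 allocation", with EAD of 0.20 (OCS) and 0.25 (Control) and 80% power, and reports that "the required sample size was determined to be 144 transplanted recipients per treatment group, or 288 total transplanted subjects". The distance to the margin is 0.075 − (0.20 − 0.25) = 0.125. The unpooled normal approximation gives

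n = (1.645 + 0.842)² × (0.20×0.80 + 0.25×0.75) / 0.125² = 137.5, so 138 per group.

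The exact unconditional test on the Farrington–Manning score, named in the protocol synopsis, has power 79.9% at 140, 80.5% at 142 and 81.0% at 144 per group. The stated 144 is therefore reproduced closely under the synopsis method, and the plan's inputs can be used below.

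**2. Effect on the observed rate.** Let m be the share of the whole arm that is lost, all of it EAD-free. The observed rate is p/(1 − m). This is an upper bound. If lost recipients have EAD risk q, the rate is (p − mq)/(1 − m). For OCS at m = 5%: q = 0 gives 0.200/0.95 = 0.2105; q = 0.10 gives 0.195/0.95 = 0.2053; q = 0.20 gives 0.190/0.95 = 0.200, that is, no bias.

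**3. Samples missed at random.** Suppose a share s of the arm misses day 7 regardless of outcome, and a fraction a of EAD is already settled by AST or PNF. The observed rate is [p − s·p(1 − a)] / [1 − s(1 − p·a)]. With p = 0.20 and s = 5%:
- a = 1: 0.200/0.960 = 0.2083
- a = 0.5: 0.195/0.955 = 0.2042
- a = 0: 0.190/0.950 = 0.2000

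So the rate rises even under random loss, unless AST and PNF settle no cases. The documents do not give a.

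**4. Imputation.** The SAP 5.3 model contains treatment but no AST, earlier bilirubin or INR, or discharge date. It therefore fills lost recipients at about the observed rate of their arm, which is the already inflated rate, and the bias remains.

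**5. Effect on the test.** Full binomial enumeration of the asymptotic Farrington–Manning score test, margin 0.075, one-sided 5%, 150 per arm before loss, upper-bound model of step 2. Power uses true rates of 0.20 and 0.25; type I error uses true rates of 0.325 and 0.25.

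| Lost from one arm | n left in that arm | OCS EAD if OCS loses | Power, OCS loss only | Control EAD if Control loses | Type I error, Control loss only |
|---|---|---|---|---|---|
| 0% | 150 | 0.2000 | 83.1% | 0.2500 | 5.1% |
| 2.5% | 146 | 0.2051 | 79.2% | 0.2564 | 6.5% |
| 5% | 142 | 0.2105 | 75.2% | 0.2632 | 8.1% |
| 10% | 135 | 0.2222 | 65.3% | 0.2778 | 12.9% |

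If both arms lose 5%, the rates are 0.2105 and 0.2632. The difference is then −0.0527 instead of −0.050, and power is 81.2%. Differential loss is what matters.

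**The case against.** The strongest reply is that nothing need be lost. Day-7 collection is mandatory and does not end at discharge. Appendix 2 keeps the day-7 column apart from the discharge column, and SAP 7 lists day 7 as a scheduled evaluation. A recipient at home is still due the sample, and missing it is a deviation. This stands, and it means that the loss may be small.

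The sentence after the quoted one in Protocol 7.2 lets evaluations extend over several days, which leaves some doubt about how strict day 7 is. A missing component could also be scored as not met, in which case the rate would not be inflated. Both are possible readings, but neither document adopts either as a rule for EAD. That is a reason to write one.

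Per Protocol exclusions are decided in a blinded committee review before lock (SAP 6.1), so exclusion is not automatic. mITT analyses with imputation are also planned. The review has no stated criterion for this case, however, and the mITT imputation uses the same model. The tipping-point analysis does not help: it cannot correct a rate biased against OCS, and it never varies missing Control outcomes. The Medical Monitor's review of site-reported EAD (Protocol 14.9) does not supply a missing negative.

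A reader might infer from the feasibility table in Protocol 1.4.4 that 5% of OCS and none of Control will be lost, because hospital stay was 12 (6–34) days with perfusion and 14 (8–88) with cold storage. The table does not support that. The 6 is the minimum of a range in 20 patients on another device with matched controls, so it shows at least 1 of 20 (95% CI 0.1% to 25%) and says nothing about day-7 sampling.

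**Conclusion.** The gap is real: a strict single-day rule, a composite whose negatives alone depend on that day, no derivation rule for a missed or off-day value, and missing-data routes that can each overstate EAD in the affected arm. The direction within an arm follows from the structure of the endpoint, provided that undetermined recipients are set aside or imputed as the plan describes.

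The size is not known, because the documents give no rate of missed day-7 samples. The tabulated figures are illustrations that assume loss in one arm only and no EAD among the lost. They are upper bounds for each share lost.

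The stronger reading, that early-discharged recipients do lose the outcome and that EAD is inflated in the arm that goes home sooner, is not supported. It would require mandatory samples to be missed, the missed composite to be treated as missing, and unequal loss between arms, and the documents establish none of these. Nor is the bias only against OCS; loss in Control works the other way. The point merits a change before lock, with medium confidence in its practical importance.

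**What to change.** Amend SAP 4.1, 5.3, 6.1 and 12.1 before database lock:

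1. If there is no day-7 bilirubin or INR, use the value nearest to day 7 within postoperative days 6–8. Use no earlier value, including a last pre-discharge value from before day 6.
2. Do not exclude a recipient from Per Protocol solely because the day-7 bilirubin or INR is off-day or missing.
3. For recipients still undetermined, impute the bilirubin/INR component conditional on the known AST and PNF status and on the latest bilirubin and INR, in place of imputing the whole composite from baseline covariates.
4. Report off-day and missing day-7 values by arm. Add a sensitivity analysis that treats off-day values as missing, and a tipping-point analysis that varies missing outcomes in both arms.

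The cost is SAP wording and modest programming. A few outcomes will rest on a sample one day from day 7, which the counts and the sensitivity analysis make visible. Some values may have to be taken from the hospital record, since the protocol specifies bilirubin and INR for EAD only on day 7. The trial is unblinded, so the rule should be fixed without reference to outcomes by arm.
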